9.1 Adverse Events

An AE is defined as any untoward medical occurrence in a study subject who is administered a pharmaceutical product that does not necessarily have a causal relationship with this product. An AE can therefore be any unfavorable and unintended sign (including an abnormal laboratory finding), symptom, or disease temporally associated with the use of an investigational product (drug and/or device), whether or not related to the investigational product (see ICH guideline E2A *Clinical Safety Data Management: Definitions and Standards for Expedited Reporting*).

An ADE is an AE directly related to the use of or caused by the investigational device, such as nasal irritation from the nasal prongs. An ADE should not be an event that is associated with study treatment, such as desaturation. ADEs are treated the same as all other AEs. For serious ADEs, see unanticipated adverse device effects (UADE) in Section 9.1.5.

All AEs and ADEs ongoing at the final visit must be followed by the PI until resolution, or for at least 30 days post 36 weeks PMA.

Documentation of AEs in the eCRF must include the following parameters; (1) duration (time of onset and resolution), (2) severity, (3) outcome, (4) action taken, and (5) relationship to study drug and/or device. AEs will be coded using the Medical Dictionary for Regulatory Activities (MedDRA).

The term “sepsis” (or a variant of that term, such as “clinical sepsis”) will be used if the subject has a diagnosis consistent with sepsis. However, if it is later determined that the subject does not have sepsis, the terms that describe the subject’s symptoms should be used instead, such as “fever” or “leukocytosis”; the terms “rule-out sepsis” or “suspected sepsis” cannot be used.

The standard of care use of nCPAP for respiratory support of preterm neonates include the following inherent risks: excess air in the stomach, redness or irritation of the nose, congestion or runny nose, and pneumothorax. If any of these occur, and the PI determines that it was likely caused by nCPAP, it should be not be considered related or possibly related to the investigational treatment.

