2.3.2.2 Study 03-CL-1401

Study 03-CL-1401 was a Phase 2a, multicenter, randomized, open-label, controlled dose-escalation study assessing the safety and tolerability of lucinactant for inhalation in preterm neonates 26 to 28 completed weeks PMA. The study design and objectives were substantially the same as Study 03-CL-1201 (Section 2.3.2.1), but in a lower gestational age population. Theoretical inhaled doses of 50, 75 and 100 mg TPL/kg were investigated and compared to subjects receiving standard therapy with nCPAP alone in a dose escalation manner. One repeat treatment was possible for all dosages (with a 2-hour minimum interval between treatments).

A total of 22 study sites from the US, Canada, Poland and Chile participated in the study. A total of 48 subjects were enrolled, with 8 each in the 50, 75 and 100 mg TPL/kg groups, and 24 in the control group. The study was terminated prior to subject enrollment for Dosing Group IV for administrative reasons (including resource limitations and the intent to study the 26-28 GA weeks PMA patients in an amendment to Study 03-CL-1202).

Active and control subjects were generally similar with respect to gestational age, birth weight, gender, race and ethnic origin. All active subjects received at least one treatment, and 16 (67%) received a repeat treatment.

Safety

Primary safety and tolerability measures included AEs, air leak, complications of prematurity, survival, and early withdrawal from the study.

All subjects experienced at least 1 TEAE. The most common TEAEs were neonatal apnea, neonatal anemia, neonatal jaundice, constipation, and neonatal RDS. There were 2 adverse device effects (ADEs) reported in this study: 1 subject in the 50 mg TPL/kg group experienced nasal

inflammation considered unrelated to study treatment, and 1 subject in the 100 mg TPL/kg experienced oxygen desaturation considered related to study treatment. Both events were considered mild.

Two deaths occurred during the course of the study. One subject in the 50 mg TPL/kg group experienced severe necrotizing enterocolitis (NEC) and died abruptly at approximately 6 weeks of life. One subject in the 75 mg TPL/kg group experienced pneumoperitoneum approximately 5 days after study treatment and died approximately 10 days after study treatment. Neither death was related to study treatment.

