In a prior clinical study using aerosolized lucinactant for inhalation via the ADS (Study 03-Cl-1201, Section 2.3.2), the incidence of AEs was similar in subjects receiving active treatment compared to controls and were as expected for this population of premature neonates. The 3 most common AEs were neonatal jaundice, constipation and neonatal apnea, and the 3 most common peri-dosing events were transient desaturation in 5 (13%) subjects, nasal irritation in 2 (5%) subjects, and vomiting in 2 (5%) subjects. Obstruction of the nares or upper airway by condensed aerosol is a theoretical risk but was not observed in Study 03-CL-1201. To mitigate the risk of airway obstruction, all subjects were continuously attended by a qualified clinician during dosing and are continuously monitored for SpO₂ and transcutaneous PCO₂. Although the drug product is heated during aerosolization, it cools to 23-38° C during delivery and the ADS will shut down if aerosol temperature is > 38° C; thermal injury to neonates was not observed in Study 03-CL-1201. The volume of aerosolized fluid administered to neonates could, in theory, affect fluid and electrolyte balance; however, no such problems were observed in Study 03-CL-1201 and electrolytes will be assessed in the present study.

Risk of air leak was 23% in active treatment subjects vs 18% (23% based on independent radiologist review) among controls. Experience with repeated dosing is limited to 3 subjects in Study 03-CL-1201; although each received dosages higher than planned for the present study, incidence of AEs in these 3 subjects was similar to that in the remainder of the cohort.

Automatic shutdown of the ADS was uncommon in study 03-CL-1201 (10% of subjects) and mostly (3/4 shutdowns) occurred at the highest dosage; only 1 shutdown occurred at a dosage (75

mg TPL/kg) similar to that proposed in the present study. All shutdowns resulted from error codes, and none resulted in any AE being reported. All subjects maintained nCPAP and inspiratory flow during active treatment, demonstrating the important safeguard that nCPAP is maintained even if the ADS fails. One ADE of nasal inflammation occurred; no other device-related performance issues resulted in any harm to subjects. A complete qualitative risk assessment has been completed to identify and mitigate potential safety risks associated with use of the ADS.

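### Protocol 9.1 keeps desaturation out of the adverse device effect category even when the device causes it, and leaves open whether the nCPAP interface is part of the investigational device

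*Protocol*

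**What the plan says.** Protocol 9.1 gives three rules that bear on device events.

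- The definition: "An ADE is an AE directly related to the use of or caused by the investigational device, such as nasal irritation from the nasal prongs".
- The exclusion that follows it: "An ADE should not be an event that is associated with study treatment, such as desaturation".
- A rule on the inherent risks of standard nCPAP, listed as "excess air in the stomach, redness or irritation of the nose, congestion or runny nose, and pneumothorax". If one of these occurs and "the PI determines that it was likely caused by nCPAP, it should be not be considered related or possibly related to the investigational treatment".

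Protocol 6.4 says that the study treatment consists of the drug and the ADS. Protocol 8.7.1 describes the study nCPAP device and interface as supplied by the sponsor for use with the ADS, and 8.7.3 describes them as commercially available. Under 6.4.2, control infants have the same nCPAP and airway connector, but the ADS is neither powered on nor connected.

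SAP 6.3 equates device-related treatment-emergent events with ADEs and summarizes them both with all adverse events and separately. Table 6.4 is the ADE table.

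**The concern.** In a drug-device combination the device delivers the study treatment, so an event can be associated with the treatment precisely because the device caused it. The exclusion does not allow for this. It names desaturation without exception, and desaturation is a plausible sign of several device problems that the protocol itself records or foresees.

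The nasal wording raises a separate question. Prongs belong to the nCPAP interface, not to the aerosol generator. If the interface is not part of the investigational device, the model example of an ADE is an nCPAP event, and a control infant never connected to the ADS can meet it. If it is part of the device, the nCPAP rule needs to be read alongside that. The protocol does not say which applies.

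Device performance is part of the stated objective (Protocol 4.1) and ADEs are a safety endpoint (4.4). At stake is whether the ADE table means what its title says.

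**Working it through.** No power, alpha or sample size figure depends on this point. The check is a comparison of the text, with a recount of earlier ADEs.

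**1. Definition against exclusion.** Under 9.1 an ADE is caused by the device. Under 6.4 the study treatment includes the device. Substituting the second into the exclusion, an ADE should not be an event associated with the drug and the device. That conflicts with the definition. Reading study treatment as the drug alone removes the conflict in general, but desaturation is still barred by name.

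**2. Can the device cause desaturation?** Protocol 3.2.4.2 names airway obstruction by condensed aerosol as a theoretical risk, mitigated partly by SpO2 monitoring. Protocol 8.8 records tubing detachments, condensate obstruction and inability to maintain nCPAP. Protocol 8.7.3 says that brief loss of positive pressure may lead to derecruitment and deterioration. That these would show as desaturation is an inference, but a direct one.

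**3. Earlier practice.** In Study 03-CL-1401 (Protocol 2.3.2.2) there were 2 ADEs among 24 active infants. One was nasal inflammation, judged unrelated to study treatment. The other was in an infant who "experienced oxygen desaturation considered related to study treatment". Section 9.1 now excludes that second combination.

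| Reading of 9.1 applied to 03-CL-1401 | ADEs | Per 24 active infants |
|---|---|---|
| As reported | 1 + 1 = 2 | 2/24 = 8.3% |
| Desaturation barred | 2 − 1 = 1 | 1/24 = 4.2% |
| Nasal event also removed by the nCPAP rule | 1 − 1 = 0 | 0% |

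The last row is not supported. The nasal event counted as an ADE while judged unrelated to study treatment, so the sponsor has kept relatedness and ADE status apart.

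**4. How common is the excluded event?** In Study 03-CL-1201, transient desaturation was the most frequent peri-dosing event: 5 of 40 active infants, 5/40 = 12.5%, stated as 13% (Protocol 3.2.4.2). The documents do not say how many were device-caused. That study's ADE entry reads "One ADE of nasal inflammation occurred"; the desaturation rule does not touch it.

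**5. Scale of this study.** The SAP reports 12 infants enrolled. One infant reclassified is 1/12 = 8.3% of the total, and a larger share of one treatment group.

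**6. Is there another route to device attribution?** Protocol 9.1 asks for the relationship to drug and/or device. However, every category in 9.1.1 is worded for the study drug, and SAP 6.3 treats device-related and ADE as one thing. A site could mark a desaturation as device-related on the form while following the instruction that it should not be an ADE. The documents do not say which prevails.

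**The case against.** The best defense is that these events are not lost. Desaturation within 2 hours of starting treatment, and nasal irritation, are adverse events of special interest (Protocol 9). The SAP summarizes peri-dosing events and prong complications (6.3.1), later desaturation (6.3.2), and events by whether they were device-related (6.3.3). Device faults have their own summary (SAP 5). The exclusion may have been meant only to separate the effects of receiving treatment from those of the hardware, and Appendix 1 does define study treatment as receipt of active or sham treatment. All of this limits the harm. It does not remove it: the special-interest summaries carry no device attribution, and the device-related summary has the ambiguity in step 6.

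Several stronger inferences are tempting and do not hold.

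- **That 9.1 both requires and forbids nasal irritation as an ADE.** Prong irritation is an example. The nCPAP sentence depends on the investigator's judgment and concerns relatedness, not ADE status.
- **That every ADE described individually in 03-CL-1201 and 03-CL-1401 would disappear.** Only the one desaturation is excluded by name.
- **That unanticipated-device-effect reporting is weakened.** Protocol 9.1.5 has its own definition, which includes effects associated with a device, and 9.1.4 requires notification of every serious event within 24 hours whatever its cause.
- **That an arm comparison is compromised.** SAP 6.3 plans none for treatment-emergent events.
- **That the count will not be comparable with Study 03-CL-1202.** Protocol 2.3.2.3 gives 10 ADEs for that study and 3.2.4.2 gives 29, and neither lists the types, so it cannot serve as a benchmark.
- **That these are the events the device is most likely to cause.** Protocol 3.2.4.1 lists nasal irritation and desaturation as known risks of nCPAP alone.

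**Conclusion.** The point holds as a classification defect. Followed as written, 9.1 leaves a device-caused desaturation out of the ADE summary, contrary to its own definition and to how Study 03-CL-1401 classified such an event. It also leaves the status of the nCPAP interface unstated, so prong events in either arm can be classified in more than one way.

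The size is modest: one of the two 03-CL-1401 ADEs, and in this study whatever desaturations among 12 infants were device-caused, a number the documents do not give and which may be zero. Collection of adverse events and expedited reporting are unaffected. The conclusion assumes that sites applied the exclusion as worded and that the SAP builds Table 6.4 from events classified under 9.1.

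**What to change.** 1. Delete the sentence in 9.1 that excludes desaturation, so that any adverse event judged caused by the ADS or its connection is an ADE, whether or not it is also attributed to the drug.
2. Keep the nCPAP sentence, since removing it would mix nCPAP events further into the device count. State whether the nCPAP interface is part of the investigational device. If it is not, replace the prong example with an event tied to the ADS.
3. Apply the causality scale in 9.1.1 separately to drug and to device.
4. Show Table 6.4 for the 12 infants twice: as classified under the current text, and under the revised rule.

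The cost is a text change and a small re-review of adverse events. The re-review would be made after enrollment ended and should be labeled as such. Showing both classifications lets the reader see what it changed. The ADE count may rise.

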9.1.1 Causal Relationship of Adverse Events

The relationship of an AE (and ADE) to a study drug is assessed by the PI or blinded designee using the following definitions:

- Not related: The AE is clearly related to other factors, such as the subject's clinical state, therapeutic interventions, or concomitant drugs.
- Unlikely Related: The AE was most likely produced by other factors, such as the subject's clinical state, therapeutic interventions, or concomitant drugs, and does not follow a known response pattern to the study drug.
- Possibly Related: The AE follows a reasonable sequence from the time of drug administration and/or follows a known response pattern to the study drug, but could have been produced by other factors, such as the subject's clinical state, therapeutic interventions, or concomitant drugs. An AE that is determined to be due to the subject's underlying disease state or is common for this patient population generally should not be considered possibly related.
- Related: The AE follows a reasonable temporal sequence from the time of the drug administration and meets the following criteria;
 - a) Follows a known response pattern to the study drug
 - b) Cannot be reasonably explained by other factors such as the subject's clinical state, therapeutic interventions, or concomitant drugs
 - c) Meets one or more of the following:
 - occurs immediately following study drug administration
 - improves on stopping the drug
 - reappears on repeat exposure
 - there is a positive reaction at the application site

An AE that is determined to be due to the subject's underlying disease state or is common for this patient population generally should not be considered related.

9.1.2 Severity Grade Levels of Adverse Events

The severity of an AE is assessed by the PI using the following definitions:

- Mild: Events require minimal or no treatment and do not interfere with the subject's daily activities
- Moderate: Events result in a low level of inconvenience or concern with the therapeutic measures. Moderate events may cause some interference with functioning.
- Severe: Events interrupt a subject's usual activity level and may require systemic drug therapy or other treatment and may be potentially life-threatening or incapacitating. Of note, the term "severe" does not necessarily equate to "serious."

9.1.3 Adverse Event Procedures

All AEs (and ADEs) are to be assessed in all subjects throughout the study period (from enrollment to study withdrawal or completion) and documented in the study eCRF. Each AE should be reported spontaneously or in response to general, non-directed discussion with the attending nurse or physician (eg, has there been any change in subject status since the last assessment period?). For each AE, the investigator should obtain all information required to complete the AE page of the eCRF, in accordance with eCRF completion guidelines (provided separately by Windtree).

All AEs, regardless of seriousness, severity, or relationship to study participation, must be recorded (using medical terminology) in the source document and on the AE page of the eCRF. Whenever possible, diagnoses should be given when signs and symptoms are due to a common etiology.

All AEs must be followed until resolution or until a stable clinical end-point is reached, or for at least 30 days after the subject's last day in the study if an AE is ongoing at the time the subject completes the study. All measures required for AE management and the ultimate outcome of the AE must be recorded in the source document and reported on the AE page of the eCRF.

9.1.4 Serious Adverse Events

An SAE is any untoward medical occurrence that meets one of the following criteria (ICH E2A, *Clinical Safety Data Management: Definitions and Standards for Expedited Reporting*):

1. Results in death
2. Is life-threatening
3. Requires inpatient hospitalization or prolongation of existing hospitalization
4. Results in persistent or significant disability/incapacity
5. Is a congenital anomaly/birth defect
6. May be considered serious when based upon appropriate medical judgment

When the investigator or trained designee becomes aware of an SAE, Windtree must be notified as soon as possible (and no later than 24 hours after the event has occurred) via telephone or email, regardless of the relationship (or lack thereof) of the SAE to study participation.

SAEs can be reported to the Windtree SAE reporting line (see Study Manual). In addition, all SAEs will be reported to the President of the Office for Registration of Medicinal Products, Medical Devices, and Biocidal Products in Poland in a timely manner, in particular, in accordance to the article #51 of the act about medical products dated 20 May 2010.

When reporting SAEs, the following information should be provided:

1. Study identifier
2. Study center
3. Subject number
4. A description of the event
5. Date of onset
6. Current status
7. Clarification on whether study aerosol was discontinued
8. The reason why the event is classified as serious
9. The Investigator's assessment of the association between the event and study participation

All reports of SAEs must be followed up within 24 hours (or sooner at the request of the medical monitor) by the completion of the SAE form and signature by the person who completed the form and the PI.

In accordance with Windtree's standard operating procedures (SOPs) and regulatory agency (eg, FDA) regulations, investigators will be notified of the occurrence of serious, unexpected, related AEs. The PI must promptly inform the relevant IRB/IEC in accordance with ICH E6 of all AEs that are deemed related to study participation (ie, there is a reasonable possibility that the AE may have been caused by the drug or device) and are thus deemed a significant new AE or risks with respect to the drug or device.

9.1.5 Unanticipated Adverse Device Effects

An UADE is defined as any serious adverse effect on health or safety or any life-threatening problem or death caused by, or associated with, a device, if that effect, problem, or death was not previously identified in nature, severity, or degree of incidence in the investigator's brochure, or any other unanticipated serious problem associated with a device that relates to the rights, safety, or welfare of subjects.

In such cases, Windtree must be notified as soon as possible (and no later than 24 hours after the event has occurred) through the following procedures:

- Contact the unblinded clinical site monitor or designated contact person regarding the event.
- Complete all device reporting procedures detailed in the study manual.

9.2 Safety Reporting

Safety report distribution is the responsibility of Windtree or designee (ie, CRO), which coordinates distribution of safety reports to applicable regulatory authorities and ECs. Finalized

safety reports are distributed by one or more individuals, “Responsible Team,” within a department that has responsibility to coordinate the distribution/submission activities, either directly or via a Local Submitting Party on behalf of Windtree.

The Responsible Team receives finalized safety reports (eg, CIOMS-I form/MedWatch 3500A/E2B file/DSUR/SUSAR Listing/PSUR/PADER) and coordinates distribution to all applicable regulatory authorities and ECs. Distribution will be done in accordance with project-specific documents, regulatory requirements, other applicable reference sources (eg, Clinical Trial Management System [CTMS] output), and applicable Windtree or designee safety procedural documents.

In addition, Windtree coordinates translation when required for safety reporting. Windtree also coordinates transcription (eg, manual transfer of information from one reporting format to another) when required. Project specific information is used to identify appropriate recipients. Quality checks will be performed on the distribution documents and recipient information for completeness and accuracy prior to distribution.

9.3 Windtree Contact Information

The names, telephone, and email numbers of the individuals who should be contacted regarding trial-related questions and safety are listed below and are provided in the communication plan included in the study manual.

9.3.1 Trial-Related Questions

For trial-related questions, such as study conduct, please call your clinical site monitor. For device- and drug-related issues, please refer to the communication plan.

